2.9.1.2 Secondary Endpoints

Secondary endpoints will be:

- First secondary test: A short tirofiban regimen of a high-dose bolus plus a shortened infusion duration is non-inferior to label-dosing eptifibatide among patients undergoing PCI with respect to the following list:
 - death, PPM or uTVR within 48 hours following PCI or hospital discharge, whichever comes first
 - PPM within 48 hours following PCI or hospital discharge, whichever comes first
 - uTVR within 48 hours following PCI or hospital discharge, whichever comes first
 - death within 48 hours following PCI or hospital discharge, whichever comes first
 - death, PPM, uTVR or major bleeding within 48 hours following PCI or hospital discharge, whichever comes first, where PPM is defined as at least one troponin elevation of ≥ 10 times the upper limit of normal and at least 20% of greater than the baseline troponin value, per the troponin Local Laboratory within 48 hours following PCI or hospital discharge, whichever comes first (a non-inferiority margin of 12.4% will be used for the short tirofiban versus eptifibatide comparison)
 - at least one troponin elevation of ≥ 10 times the upper limit of normal and at least 20% of greater than the baseline troponin value, per the troponin Local Laboratory, within 48 hours following PCI or hospital discharge, whichever comes first (a

noninferiority margin of 12.4% will be used for the short tirofiban versus eptifibatide comparison)

- at least one troponin elevation of ≥ 20 times the upper limit of normal and at least 20% of greater than the baseline troponin value, per the troponin Local Laboratory, within 48 hours following PCI or hospital discharge, whichever comes first
 - at least one troponin elevation of ≥ 50 times the upper limit of normal and at least 20% of greater than the baseline troponin value, per the troponin Local Laboratory, within 48 hours following PCI or hospital discharge, whichever comes first.
- Co-secondary tests:
- (i) a short tirofiban regimen of a high-dose bolus plus a 1-2 hour infusion duration post procedure is non-inferior to a long tirofiban regimen of a high-dose bolus plus a 12-18 hour infusion, and
 - (ii) a long tirofiban regimen of a high-dose bolus plus a 12-18 hour infusion is non-inferior to label-dosing eptifibatide with respect to the same secondary tests in the list above.

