3.10 Analysis of the Study Endpoints

3.10.1 Analysis of the Primary Endpoint

To evaluate the effectiveness of tirofiban versus eptifibatide, we look at the proportion of patients with at least one of the following endpoint measurements: death, PPM, uTVR or REPLACE-2 Major bleeding within 48 hours following PCI or hospital discharge, whichever comes first. For each pairwise comparison:

- The short tirofiban group is non-inferior to the eptifibatide group;
- The short tirofiban group is non-inferior to the long tirofiban group;
- The long tirofiban group is non-inferior to the eptifibatide group;

The following hypothesis will be tested:

$$H_0: C - T \leq -0.191$$

$$H_1: C - T > -0.191$$

To test this hypothesis, the difference ($C - T$) and its associated one-sided 97.5% confidence interval will be calculated. If the lower bound of the interval is greater than -0.191, the non-inferiority will be claimed. In order to compute the risk (proportion) difference for data with binary

response (“Yes” vs. “No”), a bivariate logistic regression will be performed for each pairwise comparison with the following specifications:

- The dependent variable will be “composite endpoint” and the independent factor will be “treatment group”;
- The risk (proportion) difference between two methods as well as its confidence interval will be estimated;
- The non-inferiority margin is 19.1%

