3.10.2 Analysis of the Secondary Endpoints

The analysis of the secondary endpoints will be conducted in the same way as for the primary endpoint.

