- *Secondary outcome 2: PPM within 48 hours following PCI or hospital discharge, whichever comes first*
- *Secondary outcome 3: uTVR within 48 hours following PCI or hospital discharge, whichever comes first*
- *Secondary outcome 4: death within 48 hours following PCI or hospital discharge, whichever comes first*
- *Secondary outcome 5: death, PPM, uTVR or major bleeding within 48 hours following PCI or hospital discharge, whichever comes first, where PPM is defined as at least one troponin elevation of ≥ 10 times the upper limit of normal and at least 20% of greater than the baseline troponin value, per the troponin Local Laboratory within 48 hours following PCI or hospital discharge, whichever comes first (a non-inferiority margin of 12.4% will be used for the short tirofiban versus eptifibatide comparison)*
- *Secondary outcome 6: at least one troponin elevation of ≥ 10 times the upper limit of normal and at least 20% of greater than the baseline troponin value, per the troponin Local Laboratory, within 48 hours following PCI or hospital discharge, whichever comes first (a noninferiority margin of 12.4% will be used for the short tirofiban versus eptifibatide comparison)*
- *Secondary outcome 7: at least one troponin elevation of ≥ 20 times the upper limit of normal and at least 20% of greater than the baseline troponin value, per the troponin Local Laboratory, within 48 hours following PCI or hospital discharge, whichever comes first*
- *Secondary outcome 8: at least one troponin elevation of ≥ 50 times the upper limit of normal and at least 20% of greater than the baseline troponin value, per the troponin Local Laboratory, within 48 hours following PCI or hospital discharge, whichever comes first*

Note: This table will also be repeated for Per-Protocol Population.

Table 17. Bivariate Logistic Regression Model for Secondary Outcomes – mITT Population

Parameter	Level	Estimate	Standard Error (SE)	Odds Ratio (OR)	95% CI for OR	Risk (Proportion Difference)	Standard Error (SE) of Risk Difference	95% CI for Risk Difference	p-value *
Secondary outcome	Short Tirofiban vs. Eptifibatide								
Secondary outcome	Short Tirofiban vs. Long Tirofiban								
Secondary outcome	Long Tirofiban vs. Eptifibatide								

* p-value is the overall p-value from the logistic regression model.

Note: The definitions of secondary outcomes are:

- *Secondary outcome 1: death, PPM or uTVR within 48 hours following PCI or hospital discharge, whichever comes first*

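### Death alone and urgent target vessel revascularization alone go through the primary's logistic model with no sparse-data rule, so an arm with no events gives unusable logistic output and, with the usual interval, overstated precision

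*SAP*

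**What the plan says.** SAP 3.10.1 sets the primary method: "a bivariate logistic regression will be performed for each pairwise comparison", with the composite endpoint as the outcome and treatment group as the only factor. On the interval it says "The risk (proportion) difference between two methods as well as its confidence interval will be estimated", and that for the difference C − T "its associated one-sided 97.5% confidence interval will be calculated". No formula is named (delta, score or bootstrap).

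SAP 3.10.2 carries this to the secondary endpoints in one sentence: "The analysis of the secondary endpoints will be conducted in the same way as for the primary endpoint". Protocol 9.6 has the same sentence. The list in SAP 2.9.1.2 includes uTVR on its own and "death within 48 hours following PCI or hospital discharge, whichever comes first".

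Mock Table 17 in SAP section 6 is titled "Bivariate Logistic Regression Model for Secondary Outcomes" and covers all eight secondary outcomes. It has columns for the estimate, its SE, the odds ratio and its CI, the risk difference with SE and CI, and a p-value described as the overall one from the logistic model.

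SAP 3.13 says only that missing data are not imputed. A small-count method, Fisher's mid-p, is specified in SAP 3.10.3, but only for the binary safety outcomes.

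**The concern.** The method was chosen for a composite expected in 51% of patients. Death or uTVR within 48 hours or by discharge will be far rarer, and an arm with no events is a realistic result, most of all in the smaller long tirofiban arm. Maximum-likelihood logistic regression has no finite solution there, and a Wald-type interval treats an observed rate of zero as known without error.

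Death and uTVR are the gravest components. Readers will look at how much excess harm the data can exclude, and the planned table could overstate that. The trial is open-label, so a method picked after the empty cells have been seen would be hard to defend.

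**Working it through.** **The plan's own figures.** The documents give no calculation for death or uTVR. The sample size for the first primary test can be reproduced: n per arm = 2p(1−p)(z₀.₉₇₅ + z₀.₉₉)²/margin² = 2 × 0.51 × 0.49 × (1.960 + 2.326)²/0.191² = 251.7, so 252 per arm or 504 in total, against about 500 stated. The design is built around a common outcome.

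**Arm sizes (assumed).** Pairwise totals of about 500, 350 and 350 (SAP 2.4) imply 250, 250 and 100. These sum to 600, while the stated total is about 550, which would leave about 50 in the long arm. I use 250 and 100.

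**Event rates (assumed, 0.1% to 1%).** Neither document gives a rate for death or uTVR. The nearest anchor is the 383-patient trial of high-dose-bolus tirofiban against abciximab in protocol 1.4.2. Its 30-day composite less its MI component leaves 6.9 − 5.9 = 1.0% and 8.8 − 7.7 = 1.1% for death and urgent revascularization together. That is rough, and over a much longer window.

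**Chance of an empty arm.** P(at least one empty) = 1 − [1 − (1−p)^n₁][1 − (1−p)^n₂]. P(both empty) = (1−p)^(n₁+n₂).

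| Rate in both arms | At least one empty, 250 v 250 | At least one empty, 250 v 100 | Both empty, 250 v 250 |
|---|---|---|---|
| 0.1% | 95% | 98% | 61% |
| 0.2% | 84% | 93% | 37% |
| 0.5% | 49% | 72% | 8% |
| 1% | 16% | 42% | 1% |

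**What the logistic model returns.** For 0/250 v 1/250, the fitted log-odds in the empty arm run off to about −26 with SE about 13,700 and a separation warning. The other arm's log-odds are ln(1/249) = −5.5. The coefficient of about 20 is simply where the iterations stop. The estimate, SE, odds ratio and its CI mean nothing, and a Wald p-value from them is uninformative. Table 17 does not say which test its p-value comes from.

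**What the delta interval returns.** The point estimate of the risk difference survives. Its variance is p₁(1−p₁)/n₁ + p₂(1−p₂)/n₂, and the empty arm's term is zero. For long tirofiban 0/100 (T) v comparator 1/250 (C):

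- T − C = −0.40 points; SE = √(0.004 × 0.996/250) = 0.399 points.
- Upper limit for excess on T = −0.40 + 1.96 × 0.399 = **+0.38** points. It is the same for an empty arm of 50, 100 or 250.
- Newcombe: the Wilson upper limit for 0/100 is 3.84/(100 + 3.84) = 3.70%, and the Wilson lower limit for 1/250 is 0.07%. Upper limit = −0.40 + √(3.70² + 0.33²) = **+3.31** points. Miettinen-Nurminen also gives +3.31.
- With a long arm of 50, the score-type limit is about +6.7 to +6.8, while the delta limit stays at +0.38.

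For 0/250 v 0/250 the delta formula gives 0 to 0. A logistic fit on an outcome with a single level may print nothing. Miettinen-Nurminen gives −1.52 to +1.52 points.

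**Coverage of the nominal 95% delta interval, by exact enumeration.**

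| True rates | Arms | Coverage |
|---|---|---|
| 1% v 0.4% | 100 v 250 | 63% |
| 0.4% v 0.2% | 250 v 250 | 77% |
| 1% v 0.4% | 250 v 250 | 91% |
| equal: 0.2%, 0.5%, 1% | 250 v 100 | 99.9%, 98%, 91% |

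The first row follows from 0.99¹⁰⁰ = 0.366, the chance that the arm of 100 is empty. These are examples, not bounds.

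**Effect on the verdict.** With 0/250 on the comparator, the treated arm passes the 19.1-point margin with up to 36/250 events (14.4%) by Wald and up to 35/250 (14.0%) by Newcombe. At a handful of events both methods pass.

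**The case against.** The strongest reply is that no decision turns on this. Limits of +0.38 and +3.31 are both far inside 19.1 points, and protocol 9.6 and SAP 3.11 rest any claim on the primary endpoint whatever the secondary endpoints show. Tables 14 and 16 print counts by arm for death and uTVR, so a reader would see the zeros. All of that stands, and it limits the point to reported precision.

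It is also true that the delta interval is an assumption. A reader might infer that the plan commits to reporting 0 (0 to 0), and so claims certainty. The text does not support that: no formula is named, zero width needs both arms empty, and the software may then print nothing.

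A reader might take 63% as the typical coverage. It is one unfavourable setting, with the small arm at 2.5 times the comparator's rate. At the same rates with 250 per arm, coverage is 91%.

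A reader might extend the point to troponin ≥50 times ULN. The documents give no rate for it, and they assume 32% at ≥10 times. At a 2% rate the chance of an empty arm is only 1.3% (250 v 250) or 14% (250 v 100).

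The failure of the logistic output is not answered. It follows from the stated method whatever interval is used for the risk difference.

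**Conclusion.** The point holds as a defect in reporting. For death alone and uTVR alone, the stated model has no estimate when an arm is empty, and the plan has no alternative. Under the usual delta interval, the limit for excess harm can be too tight by a factor of about 3.31/0.38 ≈ 8.7 in the example above. How often this arises rests on assumed rates of 0.1% to 1% and assumed arms of 250 and 100. Undercoverage depends on the setting: it is severe in some, and absent or slight in others, including equal true rates. The failure of the logistic columns rests on no such assumption once an arm has no events.

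It does not follow that a non-inferiority conclusion would be wrong, since none changes at plausible counts. Nor does it follow that the primary analysis needs to change, because near 51% an empty arm is not a realistic prospect.

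**What to change.** In SAP 3.10.2 and Table 17, for death and uTVR and any other secondary endpoint with few events in an arm:

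- Report the risk difference with a score-type interval, Miettinen-Nurminen or Newcombe, named in advance. Both are available through the RISKDIFF option of PROC FREQ.
- When an arm has no events, do not print the logistic estimate, its SE, the odds ratio, its CI or the model p-value. Say so in a footnote, and show the counts.
- State what is reported when both arms have no events: the counts and the score-type interval.

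The primary analysis can stay as it is, and stratification by access site is not needed for this purpose. The cost is a few lines of SAP text, a procedure option and a change to one mock table. No data collection changes. It should be settled before the analysis is run.

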3.10.3 Analysis of Safety Endpoints

AEs will be coded using the Medical Dictionary for Regulatory Activities (MedDRA) and the following information will be summarized:

- Overall AEs will also be described according to seriousness, severity, action taken with study drug, relationship to study drug and outcome of AE.
- The total number of AEs, the total number and proportion of patients experiencing at least one AE during the treatment period will be summarized by system organ class (SOC) and preferred term (PT). To count the number of patients who experience each AE, patients experiencing the same AE multiple times will only be counted once for the corresponding PT. AEs will be tabulated presenting the SOCs alphabetically.
- AEs will also be summarized as described above for serious adverse events (SAEs).

Furthermore, the analysis of these safety endpoints will compare the incidence in the short tirofiban treatment group to the incidence in the eptifibatide group, the incidence in the short tirofiban treatment group to the incidence in the long tirofiban treatment group and the incidence in the long tirofiban treatment group to the incidence in the eptifibatide group, by using the Fisher’s mid-p test (Berry and Armitage, 1995) and Student t-test for binary and quantitative safety outcomes,

respectively. Serious adverse events will also be tabulated overall and by severity for each treatment group.

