2.4 Study Design

This is a randomized, multicenter, open-label study comparing tirofiban I.V. bolus injection followed by a maintenance infusion for the duration of the PCI procedure plus a minimum of one hour and up to a maximum of two hours post-PCI versus label-dosing eptifibatide. Patients were randomized to tirofiban or eptifibatide using a 1:1 allocation ratio. At 159 randomized patients, a 1:1:1 randomization was initiated, randomizing patients to short tirofiban, eptifibatide or long tirofiban. Enrolment in the long tirofiban arm has been completed. Patients are mandated to stay a minimum of 18 hours following PCI.

Physician-directed standard background therapies will include dual oral antiplatelet therapy with aspirin and an approved oral P2Y12 antagonist as well as antithrombotic therapy with unfractionated heparin. Physician-directed P2Y12 antagonist therapy and choice of femoral or radial access site must be pre-specified prior to randomization.

The first 159 patients were randomized to the following two treatment arms on a 1:1 basis:

1. Tirofiban (25 µg/kg bolus followed by a 0.15 µg/kg/min infusion for the duration of the PCI procedure plus a minimum of one hour and up to a maximum of two hours post-PCI).
2. Eptifibatide (180 µg/kg bolus followed by a 2.0 µg/kg/min infusion for 18 hours post-PCI [minimum 12 hours mandated], with a second 180 µg/kg bolus 10 min after the first).

The three treatment arms for enrollment after the 159th patient were:

1. Short Tirofiban (25 µg/kg bolus followed by a 0.15 µg/kg/min infusion for the duration of the PCI procedure plus a minimum of one hour and up to a maximum of two hours post-PCI).
2. Eptifibatide (180 µg/kg bolus followed by a 2.0 µg/kg/min infusion for 18 hours post-PCI [minimum 12 hours mandated], with a second 180 µg/kg bolus 10 min after the first).
3. Long Tirofiban (25 µg/kg bolus followed by a 0.15 µg/kg/min infusion for 18 hours post-PCI) [minimum 12 hours mandated].

The short tirofiban versus eptifibatide comparison involves approximately 500 patients; the short tirofiban versus long tirofiban comparison involves approximately 350 patients; and the long tirofiban versus eptifibatide comparison involves approximately 350 patients. Approximately 550 patients will be enrolled into the study.

The study procedures to take place during the course of the study are summarized in the following Schedule of Evaluations and Procedures ([Table 1](#)).

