3 STATISTICAL METHODS

3.1 Statistical Handling Policy

3.1.1 Analysis Conventions

This section details general guidelines to be used for the statistical analyses. Deviations from these general policies may be given in the specific detailed sections of this statistical analysis plan. When this situation occurs, the rules set forth in the specific section take precedence over the general conventions. The following policies will be applied to all data presentations and analyses:

- Two-tailed tests will be performed for analyses that use statistical testing with a significance level of $\alpha = 0.05$. One-tailed tests will be performed for analyses with a significance level of $\alpha = 0.025$, if applicable.
- Summary descriptive statistics will consist of the number and percentage of responses in each category for discrete variables, and the mean, median, standard deviation (SD), minimum, maximum, and 95% confidence interval for continuous variables.
- All mean and median values will be formatted to one decimal place. Standard deviation values will be formatted to two decimal places.
- All percentages will be rounded to one decimal place. Where appropriate, the number and percentage of responses will be presented in the form XX (XX.X %), where the percentage is in the parentheses.
- For any analysis output, estimates and their corresponding standard deviations and/or standard errors will be reported up to the 3rd or 4th decimal place, per the default output of SAS.
- All p-values will be rounded to 4 decimal places (SAS format p-value). All p-values that round to 0.000 will be presented as '<0.001' and p-values that round to 1.000 will be presented as '>0.999'. Any p-value ≤ 0.05 will be considered statistically significant.
- All listings will be sorted for presentation in order of treatment group, site number, subject number, and date of procedure or event, when applicable.

- When necessary for analysis purposes, partial dates will be imputed (i.e., turned into complete dates) using the most conservative approach.
- Where appropriate, all analyses and summary tables will have the population sample size for each treatment group in the column heading.
- Tables will include titles with the corresponding analysis population and footnotes describing the analyses involved, and listings of covariates included in the analyses, where relevant.
- Version 20.0 (or higher) of MedDRA will be used for adverse event and pre-treatment conditions coding.

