Profound thrombocytopenia (< 20,000 cells/ μ L), n (%)			
Yes			
No			
Length of hospital stay (hours)			

RESPONSIVE
RELIABLE
RESULTS

SAVI-PCI
Statistical Analysis Plan
Version FINAL
20 February, 2019
Page 77 of 79

Parameter	Treatment Group		
	Short Tirofiban (N=)	Short Tirofiban (N=)	Short Tirofiban (N=)
Available n			
Mean \pm SD			
95% CI for Mean			
Median (IQR)			
Min - Max			

Table 21. Fisher’s Exact Test for Binary Safety Outcomes – Safety Population

Statistic	Level	DF	Value	p-value
Fisher’ exact test	Short Tirofiban vs. Eptifibatide			
Fisher’ exact test	Short Tirofiban vs. Long Tirofiban			
Fisher’ exact test	Long Tirofiban vs. Eptifibatide			

Note: p-value is based on the Fisher’s mid-p test.

Note: The Binary Safety Outcomes are the following:

- *Bleeding events according to REPLACE-2 Major bleeding definition*
- *Bleeding events according to TIMI Major bleeding definition*
- *Bleeding events according to REPLACE-2 Minor bleeding definition*
- *Bleeding events according to TIMI Minor bleeding definition*
- *Bleeding events according to REPLACE-2 Plus Major bleeding definition*
- *Bleeding events according to TIMI Plus Major bleeding definition*
- *Sum of REPLACE-2 Major and Minor bleeding*
- *Sum of REPLACE-2 Plus Major and Minor bleeding*
- *Sum of TIMI Major and Minor bleeding*
- *Sum of TIMI Plus Major and Minor bleeding*
- *Non-bleeding adverse events*
- *Thrombocytopenia (< 100,000 cells/ μ L)*
- *Severe Thrombocytopenia (< 50,000 cells/ μ L)*
- *Profound Thrombocytopenia (< 20,000 cells/ μ L)*

Table 22. Student t-Test for Quantitative Safety Outcome – Safety Population

Statistic	Level	DF	t Value	p-value
t-test	Short Tirofiban vs. Eptifibatide			
t-test	Short Tirofiban vs. Long Tirofiban			
t-test	Long Tirofiban vs. Eptifibatide			

Note: p-value is based on the Student t-test.

Note: The Quantitative Safety Outcome is the length of hospital stay.

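### Length of hospital stay is tested with a pooled-variance t-test although the long-tirofiban arm is 2.5 to 5 times smaller than its comparators, so two of the three p-values depend on an unchecked equal-variance assumption (minor)

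*SAP*

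**What the plan says.** SAP 3.10.3 compares the arms on safety by the Fisher's "mid-p test (Berry and Armitage, 1995) and Student t-test for binary and quantitative safety outcomes". Mock Table 22 states that "The Quantitative Safety Outcome is the length of hospital stay" and gives one row, with a single DF, t value and p-value, to each of the three pairs. Its note reads "p-value is based on the Student t-test". Neither the SAP nor the Protocol names an unequal-variance version, a variance check, a transformation or a rank test. Protocol 9.6 names only the mid-p method for safety endpoints, so the t-test comes from the SAP alone.

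On sidedness, SAP 3.1.1 says "Two-tailed tests will be performed for analyses that use statistical testing with a significance level of" 0.05, and it treats any p-value at or below 0.05 as significant.

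Arm sizes are not stated directly. SAP 2.4 gives:
- "The short tirofiban versus eptifibatide comparison involves approximately 500 patients"
- "the short tirofiban versus long tirofiban comparison involves approximately 350 patients"
- "the long tirofiban versus eptifibatide comparison involves approximately 350 patients"
- "Approximately 550 patients will be enrolled into the study"

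SAP 2.4 and 2.5 add that the long arm opened after 159 patients had been randomized to the other two, and that it has closed while those two continue.

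**The concern.** The Student t-test estimates one common variance. With equal arms this does little harm even if the variances differ. With unequal arms the pooled estimate is dominated by the larger arm, while the true variance of the mean difference is dominated by the smaller one. If the smaller arm has the larger spread, the standard error is too small and the test rejects too often. If it has the smaller spread, the test rejects too rarely.

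The long arm is the smaller one in both comparisons that include it. One of these, short versus long tirofiban, is the comparison meant to isolate infusion duration, and less overnight hospitalization is among the stated reasons for a short infusion (Protocol 1.4.3, SAP 2.1). For that pair, unequal spread is conceivable. Planned infusions differ (1–2 h against 12–18 h), and short-arm patients with a persisting thrombotic complication continue for at least 12 h (Protocol 5.2.4), which makes that arm a mixture.

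**Working it through.** **1. The plan's own figure.** SAP 2.6 gives about 350 patients for each co-primary test (margin 19.1%, power 94.5%, one-sided alpha 0.025, event rate 51% in both arms). The standard formula is

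n per arm = 2p(1−p)(z₀.₉₇₅ + z₀.₉₄₅)²/margin².

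It gives 174 per arm, or 348 in total. Power at 175:175 is 94.7%. So the figure reproduces, but only with equal arms.

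**2. Arm sizes implied by the documents.** Let S, E and L be short tirofiban, eptifibatide and long tirofiban.
- From S+E = 500, S+L = 350 and E+L = 350: S = (500 + 350 − 350)/2 = 250, so E = 250 and L = 100. These sum to 600, not 550.
- From the total: L = 550 − 500 = 50.
- Equal arms of 175 do not fit: 500 + 175 = 675.

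The imbalance is therefore 250/100 = 2.5 or 250/50 = 5. The stated totals conflict, but the long arm is much the smallest on either reading.

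**3. Error rate of the pooled test.** Take the comparator SD as 1, the long-arm SD as r, n₁ = 250 and n₂ = 100 or 50.
- True variance of the mean difference: V = 1/n₁ + r²/n₂.
- Variance the pooled test expects: Vp = [(n₁ + n₂r²)/(n₁ + n₂)] × (1/n₁ + 1/n₂).
- True two-sided error ≈ 2[1 − Φ(1.96√(Vp/V))].

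Example, 250:100 and r = 1.5:
- V = 0.004 + 2.25/100 = 0.0265.
- Vp = (475/350) × 0.014 = 0.0190.
- √(Vp/V) = 0.847, and 1.96 × 0.847 = 1.66, so the error is 9.7%.

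Example, 250:50 and r = 2:
- V = 0.004 + 4/50 = 0.084.
- Vp = (450/300) × 0.024 = 0.036.
- √(Vp/V) = 0.655, and 1.96 × 0.655 = 1.283, so the error is 20.0%.

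At 250:250, Vp = V for every r, so the error stays at 5%.

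No SD of stay is given in either document, so r is an assumption, shown over a range:

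| SD ratio, long/comparator | 250:100 | 250:50 |
|---|---|---|
| 0.5 | 1.1% | 0.3% |
| 0.8 | 3.1% | 2.3% |
| 1.0 | 5.0% | 5.0% |
| 1.1 | 6.0% | 6.6% |
| 1.25 | 7.5% | 9.1% |
| 1.5 | 9.7% | 13.2% |
| 2.0 | 13.2% | 20.0% |

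Simulation with normal data (100,000 runs per cell) agrees to within about 0.1 percentage point. It gives 4.9–5.1% at 250:250.

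**4. The Welch test in the same settings.** With normal data its error is 4.8–5.1% at both 250:100 and 250:50, for every ratio from 0.5 to 2. With skewed (gamma) data, equal means and a more spread-out long arm (20,000 runs):

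| Arms, SD ratio | Pooled | Welch |
|---|---|---|
| 250:100, 1.5 | 9.6% | 5.9% |
| 250:100, 2 | 13.7% | 6.9% |
| 250:50, 1.5 | 13.1% | 7.4% |
| 250:50, 2 | 20.5% | 9.4% |

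Welch is better throughout, but it does not fully remove the effect of skewness.

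**The case against.** **No spread is documented.** A reader might infer that two of the three p-values are wrong. The documents do not support that. They support only a conditional statement, and a modest departure (ratio 1.1) moves the error to just 6.0–6.6%. This stands.

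**The infusion-duration argument covers one comparison.** A reader might infer that different infusion lengths make unequal spread likely in both long-tirofiban pairs. They do not: long tirofiban and eptifibatide have the same planned infusion of 18 h with a 12 h minimum, and SAP 2.2 says that this pair is compared at equal duration. The argument bears on short versus long tirofiban only. Even there the mandatory 18 h stay in every arm covers the planned infusion and weakens the link between infusion and discharge. This stands too.

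**A long right tail is not established.** Protocol 9.7 describes a database running from study drug administration to 48 hours or discharge. If recorded stay is confined to that window, the tail is cut. Skewness is a reasonable worry, not a documented fact.

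**Consequence is low.** Length of stay is the last listed safety item, with no hypothesis, margin or power. The primary safety endpoint is major bleeding, and SAP 3.11 ties any claim to the primary composite. The safety p-values are unadjusted in any case. Table 20 already prints each arm's mean, SD, median and IQR, so unequal spread would be visible.

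**The start of the stay.** A reader might also infer that the stay should be redefined to exclude time before the procedure. Neither document defines its start or says that such time is counted, so there is no basis here for changing the endpoint.

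None of this shows the pooled test to be the better choice. The imbalance is real on either reading of the totals, and the alternative costs almost nothing.

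**Conclusion.** The point holds in conditional form and is minor. If the SD of stay differs between arms, the pooled test is miscalibrated in the two comparisons with long tirofiban: too liberal when the long arm is more variable, too conservative when it is less so. Short tirofiban versus eptifibatide is not exposed.

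This rests on three things:
- reading an unqualified Student t-test as the pooled version, since the SAP does not print the words equal variance;
- arm sizes of about 250, 250 and either 100 or 50, inferred from totals that conflict;
- SD ratios that are assumed, because none is given.

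The actual distortion cannot be known from the documents. Nothing in the trial's decision rule depends on it.

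**What to change.** In SAP 3.10.3 and Table 22, replace the Student t-test with the Welch t-test (Satterthwaite degrees of freedom) for all three comparisons of length of stay. Add the mean difference with its 95% CI to Table 22, which now shows only DF, t and p. Prespecify a rank-based or bootstrap analysis as a supporting check, because Welch does not fully correct for skewness. Leave the definition of the outcome as it is.

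The cost is a change of SAP wording, a revised table note, extra columns in one table and one supporting analysis. No new data are needed. If the variances turn out equal, Welch loses almost nothing. Fixing the test before the analysis also removes a later choice between two versions.
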